### 6.3 Demographics and the Baseline Characteristics

Summaries of the following demographics and other baseline characteristics will be presented by group:

- Age, gender and race
- Physical examination, including temperature, height, weight and BMI,
- IgG and IgM at baseline,
- Baseline nucleic acid testing result,
- Whether it has passed the laboratory screening before enrollment

ANOVA will be used to detect the difference for age, temperature, height, weight, and BMI among groups, and group t-test will be used for those between immunization schedules. Chi-square test or Fisher exact test will be used to detect the difference for gender, race, antibody screening results, nucleic acid testing result, and whether it has passed the laboratory screening before enrollment among groups and between immunization schedules.

Descriptive statistics for the compliance will be provided by group, including whether complete all visits, whether complete all vaccinations, whether complete all safety observations, and whether complete the immunogenicity blood collections. Chi-square test or Fisher exact test will be used to detect the difference among groups and between

immunization schedules.

The counts and proportions of concomitant medication and concomitant vaccine will be summarised by group per phase and immunization schedule. Fisher exact test will be used to detect the difference among groups and between immunization schedules. Both concomitant medication and concomitant vaccines will be listed.

#### 6.4 Immunogenicity Analysis

(1) The statistical method for immunogenicity evaluation for emergency immunization schedule and routine immunization schedule in Phase I will be carried out as follows.

Taking emergency immunization schedule in Phase I as an example, the following rates will be calculated by the group and their confidence intervals will be estimated by Clopper-Pearson method:

- Rate of serum neutralizing antibody titer no less than 4 at 7 days after the first dose,
- Rate of serum neutralizing antibody titer no less than 4 at 7 days after the first dose in the subjects with antibody titer before vaccination less than 4,
- Quadruple increase rate of serum neutralizing antibody titer at 7 days after the first dose in the subjects with antibody titer before vaccination no less than 4,
- Serum neutralizing seroconversion rate-1 (bounded by 4) at 7 days after the first dose,
- Rate of serum neutralizing antibody titer no less than 8 at 7 days after the first dose in the subjects with antibody titer before vaccination less than 8,
- Quadruple increase rate of serum neutralizing antibody titer at 7 days after the first dose in the subjects with antibody titer before vaccination no less than 8,
- Serum neutralizing seroconversion rate-2 (bounded by 8) at 7 days after the first dose,
- IgG antibody positive rate at 7 days after the first dose,
- IgM antibody positive rate at 7 days after the first dose.

Chi-square test or Fisher exact test will be used to detect differences among groups per rate as above. Furthermore, if statistically significance exists, the pairwise comparison will be conducted between groups by Chi-square test or Fisher exact test.

Descriptive statistics for the following serum neutralizing antibody geometric mean titers (GMTs) and geometric mean increasements (GMIs), including geometric mean and 95% confidence interval (95% CI), will be provided by group:

- GMT and GMI at 7 days after the first dose,
- GMT and GMI at 7 days after the first dose in the subjects with antibody titer before vaccination less than 4,
- GMT and GMI at 7 days after the first dose in the subjects with antibody titer before vaccination no less than 4,
- GMT and GMI at 7 days after the first dose in the subjects with antibody titer before vaccination less than 8,
- GMT and GMI at 7 days after the first dose in the subjects with antibody titer before vaccination no less than 8.

ANOVA model with log-transformation (per GMT and GMI as above) will be used to detect the difference among groups. Furthermore, if statistically significance exists, pairwise comparison will be conducted between groups by group t-test with log-transformation. Inversetiter distributions of antibody before vaccination and at 7 days after the first dose will be plotted by group, respectively.

The statistical analysis method of immunogenicity evaluation on 14, 21, 28, 42 days after the first dose immunization of phase I emergency immunization schedule and 28, 35, 42, 56 days after the first dose immunization of phase I

routine immunization schedule was the same as that of 7 days after the first dose in emergency immunization schedule of phase I as above. Additionally, using the same method, immunogenicity comparison between emergency immunization schedule and routine immunization schedule in Phase I will be conducted by group (medium-dose group and high-dose group) at 14 days and 28 days after the whole schedule vaccination, respectively. 14 days after the whole schedule vaccination is 28 days after their first dose in emergency immunization schedule and 42 days after the first dose in routine immunization schedule, respectively. Meanwhile, 28 days after the whole schedule vaccination is 42 days after their first dose in emergency immunization schedule and 56 days after the first dose in routine immunization schedule, respectively.

(2) The statistical method for immunogenicity evaluation for emergency immunization schedule and routine immunization schedule in Phase II will be carried out as follows.

Taking emergency immunization schedule in Phase II as an example, the following rates will be calculated by the group and their confidence intervals will be estimated by Clopper-Pearson method:

- Rate of serum neutralizing antibody titer no less than 4 at 14 days after the whole schedule vaccination,
- Rate of serum neutralizing antibody titer no less than 4 at 14 days after the whole schedule vaccination in the subjects with antibody titer before vaccination less than 4,
- Quadruple increase rate of serum neutralizing antibody titer at 14 days after the whole schedule vaccination in the subjects with antibody titer before vaccination no less than 4,
- Serum neutralizing seroconversion rate-1 (bounded by 4) 14 days after the whole schedule vaccination,

days after the whole schedule vaccination in routine immunization schedule was the same as that of phase II emergency immunization schedule 14 days after the whole immunization as above. Additionally, The immunogenicity of medium-dose group and high-dose group in phase II was compared among different immunization schedules. The statistical analysis method was the same as that of the phase II emergency immunization schedule 14 days after the whole immunization.

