**Table 2 Blood collection at different time points in immunogenicity observation**

Phase and immunization schedule	Test contents	Sampling time
Phase I - emergency immunization schedule	Neutralizing antibody, IgG, IgM	Before the first dose of inoculation (D0), 7 days after the first dose of inoculation (D7), 14 days after the first dose of inoculation (D14), 21 days after the first dose of inoculation (D21), 28 days after the first dose of inoculation (D28), 42 days after the first dose of inoculation (D42), 6 months after the whole schedule vaccination (D194)
	T cell response	Before the first dose of inoculation (D0), 14 days after the first dose of inoculation (D14), 14 days after the whole schedule vaccination (D28)
Phase I - routine immunization schedule	Neutralizing antibody, IgG, IgM	Before the first dose of inoculation (D0), 28 days after the first dose of inoculation (D28), 35 days after the first dose of inoculation (D35), 42 days after the first dose of inoculation (D42), 56 days after the first dose of inoculation (D56), 6 months after the whole schedule vaccination (D208)
	T cell response	Before the first dose of inoculation (D0), 28 days after the first dose of inoculation (D28), 42 days after the first dose of inoculation (D42)
Phase II - emergency immunization schedule	Neutralizing antibody	Before the first dose of inoculation (D0), 14 days after the whole schedule vaccination (D28), 42 days after the first dose of inoculation (D42), 6 months after the whole schedule vaccination (D194)
Phase II - routine immunization schedule	Neutralizing antibody	Before the first dose of inoculation (D0), 28 days after the whole schedule vaccination (D56), 6 months after the whole schedule vaccination (D208)

This study was carried out by the Jiangsu Provincial Center for Disease Control and Prevention (Public Health Research Institute of Jiangsu Province).

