## 4.2 Endpoint of Phase II

### 4.2.1 Immunogenicity Endpoint

#### 4.2.1.1 Primary Endpoint

The main immunogenicity endpoints of emergency immunization schedule and routine immunization schedule were defined as follows:

- Emergency immunization schedule: the seroconversion rate-1 at 14 days after the whole schedule vaccination;
- Emergency immunization schedule: the seroconversion rate-2 at 14 days after the whole schedule vaccination;
- Routine immunization schedule: the seroconversion rate-1 at 28 days after the whole schedule vaccination;
- Routine immunization schedule: the seroconversion rate-2 at 28 days after the whole schedule vaccination.

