#### 4.2.1.2 Secondary Endpoint

The emergency immunization schedule at 14 days after the whole schedule vaccination and the routine immunization schedule at 28 days after the whole schedule vaccination are defined as the following secondary immunogenicity endpoint:

- (1) Post-immunization neutralization antibody  $\geq 4$  rate;
- (2) Post-immunization neutralizing antibody titer  $\geq 4$  in the subjects with pre-immunization  $< 4$ ;
- (3) The 4-time increase rate of neutralizing antibody after immunization in the subjects  $\geq 4$  before immunization;
- (4) Post-immunization neutralization antibody  $\geq 8$  rate;
- (5) Post-immunization neutralizing antibody titer  $\geq 8$  in the subjects with pre-immunization  $< 8$ ;
- (6) The 4-time increase rate of neutralizing antibody after immunization in the subjects  $\geq 8$  before immunization;
- (7) Post-immunization neutralizing antibody GMT and GMI;
- (8) Post-immunization neutralizing antibody GMT and GMI in the subjects with pre-immunization  $< 4$ ;
- (9) Post-immunization neutralizing antibody GMT and GMI in the subjects with post-immunization  $\geq 4$ ;
- (10) Post-immunization neutralizing antibody GMT and GMI in the subjects with pre-immunization  $< 8$ ;
- (11) Post-immunization neutralizing antibody GMT and GMI in the subjects with post-immunization  $\geq 8$ ;

The emergency immunization schedule at 28 days after the whole schedule vaccination is defined as the following secondary immunogenicity endpoint:

- (12) The neutralization antibody at 28 days after the whole schedule vaccination  $\geq 4$  rate;
- (13) The neutralizing antibody at 28 days after the whole schedule vaccination  $\geq 4$  rate in the subjects with pre-immunization  $< 4$ ;
- (14) The 4-time increase rate of neutralizing antibody at 28 days after the whole schedule vaccination in the subjects  $\geq 4$  before immunization;
- (15) The seroconversion rate-1 at 28 days after the whole schedule vaccination
- (16) The neutralization antibody  $\geq 8$  rate at 28 days after the whole schedule vaccination;
- (17) The neutralizing antibody at 28 days after the whole schedule vaccination  $\geq 8$  in the subjects with pre-immunization  $< 8$ ;
- (18) The 4-time increase rate of neutralizing antibody at 28 days after the whole schedule vaccination in the subjects  $\geq 8$  before immunization;
- (19) The seroconversion rate-2 at 28 days after the whole schedule vaccination

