## 6.5 Exploratory Analysis

(1) The statistical method for exploratory evaluation for emergency immunization schedule and routine immunization schedule in Phase I is summarised as follows.

The following rates will be calculated by the group and their confidence intervals will be estimated by the Clopper-Pearson method:

- Rate of serum neutralizing antibody titer no less than 4 at 6 months after the whole schedule vaccination,
- Rate of serum neutralizing antibody titer no less than 8 at 6 months after the whole schedule vaccination,
- Positive rate of T cell response (IFN- $\gamma$  detection using Elispot) at 14/28 days after the first dose in emergency immunization schedule/ routine immunization schedule,
- Positive rate of T cell response (IFN- $\gamma$  detection using Elispot) at 14 days after the whole schedule vaccination,

Chi-square test or Fisher exact test will be used to detect differences among groups per rate as above. Furthermore, if statistically significant, pairwise comparison will be conducted between groups by Chi-square test or Fisher exact test. Additionally, using the same method, their comparison between emergency immunization schedule and routine immunization schedule will be conducted by group (medium-dose group and high-dose group), respectively.

Descriptive statistics for the difference between the average number of stimulation holes for T cell response assay (IFN- $\gamma$  detection using Elispot method) and that of negative control on day 14 (emergency immunization schedule) / 28 (routine immunization schedule) after the first dose of immunization will be provided by group. Rank-sum test will be used to test the difference among groups. Furthermore, if statistically significance exists, pairwise comparison will be conducted between groups by rank-sum test.

Descriptive statistics for GMT at 6 months after the whole schedule vaccination, including geometric mean and 95% confidence interval (95% CI), will be provided by the group. Furthermore, if statistically significance exists, group t-test with log-transformation will be conducted between groups. Additionally, using the same method, T cell response assay (IFN- $\gamma$  detection using Elispot method) comparison between emergency immunization schedule and routine immunization schedule will be conducted by group (medium-dose group and high-dose group), respectively.

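### Between-schedule comparisons need a matched sampling time: the Phase II antibody comparison names none, and one Phase I T-cell comparison is set at D14 v D28, before dose 2

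*SAP*

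**What the plan says.** **Phase II antibody.** SAP section 6.4(2) states "The immunogenicity of medium-dose group and high-dose group in phase II was compared among different immunization schedules" and then "The statistical analysis method was the same as that of the phase II emergency immunization schedule 14 days after the whole immunization". No sampling time is given for the comparison itself. Section 4.2.1.1 sets the primary endpoints at different times: "Emergency immunization schedule: the seroconversion rate-1 at 14 days after the whole schedule vaccination", but "Routine immunization schedule: the seroconversion rate-1 at 28 days after the whole schedule vaccination", and likewise for seroconversion rate-2. Section 4.2.1.2 adds a later set for the emergency schedule: "The emergency immunization schedule at 28 days after the whole schedule vaccination is defined as the following secondary immunogenicity endpoint". Items 12 to 24 of that set include both seroconversion rates (items 15 and 19). Table 2 gives the Phase II antibody samples as D0, D28, D42 and D194 (emergency) and D0, D56 and D208 (routine).

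**Phase I T cells.** Section 6.5(1) lists T-cell positivity "at 14/28 days after the first dose in emergency immunization schedule/ routine immunization schedule", and again at 14 days after the second dose. It then says of all the listed rates that "their comparison between emergency immunization schedule and routine immunization schedule will be conducted by group", for the medium and high dose. Spot counts (stimulated wells minus negative control) are described only at D14/D28. The last sentence of 6.5(1) extends the T-cell assay to a comparison between schedules and names no time. Table 2 collects T cells at D0, D14 and D28 (emergency) and at D0, D28 and D42 (routine).

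**Context.** Section 2.2 makes the choice of dosage and schedule an aim of Phase II. Section 6.7 calls all p-values nominal.

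**The concern.** A comparison of two schedules is interpretable when both are sampled at the same interval after the last dose. If one is read at 14 days and the other at 28 days, any rise or fall of antibody in that fortnight is added to the schedule difference and cannot be separated from it. For Phase II the plan leaves this open in a comparison that bears on the schedule decision, so the time could be chosen after the data are seen.

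For the first T-cell time the problem is in the stated analysis. At D14 and D28 every vaccinee in a given dose group has had one dose of the same product. The interval between doses, which is what distinguishes the schedules, has not yet had any effect. The comparison can show a difference, but not one due to the schedule.

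**Working it through.** **1. Group sizes.** Phase II has 300 per schedule at 2:2:1 (section 3.1): 300 × 2/5 = 120, 120 and 300 × 1/5 = 60. Over two schedules this is 240, 240 and 120, as in section 3.3. In Phase I each dose stage has 36 per schedule at 2:1: 36 × 2/3 = 24 vaccinees, and 2 × 24 = 48 per schedule, again as in section 3.3.

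**2. Sampling days.** Dose 2 is on D14 (emergency) or D28 (routine). Adding 14, 28 or 180 days and looking each day up in Table 2 gives:

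| Time | Emergency | Routine | Matched? |
|---|---|---|---|
| Phase II, 14 days after dose 2 | D28, sampled | D42, not sampled | not possible |
| Phase II, 28 days after dose 2 | D42, sampled | D56, sampled | yes |
| Phase II, 6 months after dose 2 | D194, sampled | D208, sampled | yes |
| Phase I T cells, first time | D14 (14 days after dose 1) | D28 (28 days after dose 1) | no |
| Phase I T cells, second time | D28 (14 days after dose 2) | D42 (14 days after dose 2) | yes |

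For Phase I antibody, section 6.4(1) names 14 and 28 days after dose 2 and writes out the days for each schedule. Section 6.4(2) has no such sentence for Phase II.

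**3. Is the first T-cell sample before dose 2?** Table 1 labels the D14 (emergency) and D28 (routine) draws for blood routine, blood chemistry and inflammatory factors as taken before the second dose. Table 2 counts the T-cell samples of the same days from the first dose. Even a sample drawn later on the same day would leave dose 2 almost no time to act.

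**4. Size of a pure time effect (illustration).** The SAP gives no expected titers, rates or SDs, so all effect sizes here are assumptions. The question is how often a nominal p<0.05 would arise between schedules when only sampling time differs.

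*GMT, 120 v 120, two-sided z-test on log10 titer.* SE = SD × √(2/120); at SD 0.4, SE = 0.0516. With z = log10(r)/SE, the chance is Φ(z − 1.96) + Φ(−z − 1.96).

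| Time-only ratio r | log10 r | z at SD 0.4 | Chance | SD 0.5 to 0.3 |
|---|---|---|---|---|
| 1.2 | 0.0792 | 1.53 | 34% | 23% to 53% |
| 1.3 | 0.1139 | 2.21 | 60% | 42% to 84% |
| 1.5 | 0.1761 | 3.41 | 93% | 78% to 99.5% |

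*Rates, Fisher exact test.* The chance is the sum over all outcome pairs (i, j) with p ≤ 0.05 of the product of the two binomial probabilities.

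| Comparison | Assumed rates | Chance |
|---|---|---|
| Seroconversion, 120 v 120 | 90% v 92.5% | 7% |
| | 95% v 97.5% | 9% |
| | 90% v 95% | 22% |
| | 90% v 90% (no time effect) | 3% |
| T-cell positivity, 24 v 24 | 40% v 50% | 7% |
| | 40% v 60% | 22% |
| | 40% v 70% | 47% |
| | 50% v 50% (no time effect) | 3% |

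**The case against.** The strongest reply concerns Phase II. Section 6.4(2) carries over a method (exact intervals, chi-square or Fisher tests, log-scale ANOVA and t-tests), not a sampling day. A reader might infer that the plan requires a 14 v 28 day comparison, or that the primary variables cannot be compared at a common time. The document supports neither: it is silent on the time, and section 4.2.1.2 defines both seroconversion rates for the emergency schedule at 28 days, when the routine primary endpoints are measured. A reader might also infer that schedule comparisons are unmatched throughout. They are not: Phase I antibody, T-cell positivity 14 days after dose 2, and the 6-month times are matched.

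The T-cell rates are Phase I exploratory endpoints with 24 per dose group, and Phase II collects no T cells, so they do not enter the Phase II results. P-values are nominal. Section 7 puts the analysis tables in an appendix that is not at hand and may name a time. Finally, section 3.2.1 describes separate randomization codes for each schedule, and the SAP does not describe assignment to schedule as randomized, so matching the day would not by itself remove cohort differences.

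All of this stands and limits the point. It does not remove it. The only time that 6.4(2) mentions is one at which the routine schedule has no Phase II sample, and the matched alternative is not selected. Nominal p-values do not help either, because the estimated difference itself would be confounded with time. For the first T-cell time there is no silence to rely on: the unmatched comparison is written into the plan.

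**Conclusion.** The point holds in two parts, as a should-fix.

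- **Phase I T cells.** The planned between-schedule comparison of positivity at D14 v D28 cannot show a schedule effect; it reflects time since dose 1, or cohort. Spot counts are specified only at that time, although the matched sample is collected. This follows from the text and needs no assumption.
- **Phase II antibody.** The defect is an unstated time. A time effect could be read as a schedule effect; the document does not say that it will be.

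How often a misleading result would arise depends on assumed effects. It is small for seroconversion if rates are high and close (about 7% to 9% for a 2.5-point difference) and large for GMT if titers move by half (93% at SD 0.4). These figures show sensitivity and do not predict this trial.

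**What to change.** - **Section 6.4(2):** state that Phase II schedule comparisons by dose group use 28 days after dose 2 (emergency D42 v routine D56), and that 14-day emergency results are not compared with 28-day routine results.
- **Section 6.5(1):** drop the D14 v D28 comparison between schedules, or label it as a comparison of time since dose 1. Keep the positivity comparison already planned at 14 days after dose 2 (D28 v D42), add the spot-count comparison at that time, and name the time in the closing T-cell sentence.

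The cost is a few lines of SAP text. Table 2 already provides every sample. At most, one T-cell comparison that says nothing about the schedule is lost.

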## 6.5 Exploratory Analysis

(1) The statistical method for exploratory evaluation for emergency immunization schedule and routine immunization schedule in Phase I is summarised as follows.

The following rates will be calculated by the group and their confidence intervals will be estimated by the Clopper-Pearson method:

- Rate of serum neutralizing antibody titer no less than 4 at 6 months after the whole schedule vaccination,
- Rate of serum neutralizing antibody titer no less than 8 at 6 months after the whole schedule vaccination,
- Positive rate of T cell response (IFN- $\gamma$  detection using Elispot) at 14/28 days after the first dose in emergency immunization schedule/ routine immunization schedule,
- Positive rate of T cell response (IFN- $\gamma$  detection using Elispot) at 14 days after the whole schedule vaccination,

Chi-square test or Fisher exact test will be used to detect differences among groups per rate as above. Furthermore, if statistically significant, pairwise comparison will be conducted between groups by Chi-square test or Fisher exact test. Additionally, using the same method, their comparison between emergency immunization schedule and routine immunization schedule will be conducted by group (medium-dose group and high-dose group), respectively.

Descriptive statistics for the difference between the average number of stimulation holes for T cell response assay (IFN- $\gamma$  detection using Elispot method) and that of negative control on day 14 (emergency immunization schedule) / 28 (routine immunization schedule) after the first dose of immunization will be provided by group. Rank-sum test will be used to test the difference among groups. Furthermore, if statistically significance exists, pairwise comparison will be conducted between groups by rank-sum test.

Descriptive statistics for GMT at 6 months after the whole schedule vaccination, including geometric mean and 95% confidence interval (95% CI), will be provided by the group. Furthermore, if statistically significance exists, group t-test with log-transformation will be conducted between groups. Additionally, using the same method, T cell response assay (IFN- $\gamma$  detection using Elispot method) comparison between emergency immunization schedule and routine immunization schedule will be conducted by group (medium-dose group and high-dose group), respectively.

(2) The statistical method for exploratory evaluation for emergency immunization schedule and routine immunization schedule in Phase II is summarised as follows.

The following rates of antibody will be calculated by the group and their confidence intervals will be estimated by the Clopper-Pearson method:

- Rate of serum neutralizing antibody titer no less than 4 at 6 months after the whole schedule vaccination,
- Rate of serum neutralizing antibody titer no less than 8 at 6 months after the whole schedule vaccination,

Chi-square test or Fisher exact test will be used to detect differences among groups per rate as above. Furthermore, if statistically significant, pairwise comparison will be conducted between groups by Chi-square test or Fisher exact test.

GMT at 6 months after the whole schedule vaccination will be calculated by the group in terms of geometric mean and 95% CI. ANOVA model with log-transformation will be used to detect the difference among groups. Furthermore, if statistically significance exists, group t-test with log-transformation will be conducted between groups.

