#### 4.1.2 Exploratory Endpoint

The following exploratory endpoints were defined for emergency and routine immunization schedules, respectively:

- (1) Neutralization antibody  $\geq 4$  rate at 6 months after the whole schedule vaccination
- (2) Neutralization antibody  $\geq 8$  rate at 6 months after the whole schedule vaccination
- (3) GMT of neutralizing antibody at 6 months after the whole schedule vaccination
- (4) The positive rate of T cell response assay (IFN- $\gamma$  detection) at 14 days after the first dose of inoculation (emergency immunization schedule) or 28 days after the first dose of inoculation (routine immunization schedule)
- (5) The positive rate of T cell response assay (IFN- $\gamma$  detection) at 14 days after the whole schedule vaccination

IFN- $\gamma$  positive was defined as the average number of negative control  $< 6$ , the average number of peptide stimulation wells - negative control  $> 6$ ; or when the average number of negative control was  $\geq 6$ , the average number of peptide stimulation wells / negative control points was  $\geq 2$ .

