#### **6.9 Processing of missing data**

Concerning the statistical analysis of FAS, the missing data of the post-vaccination antibody test result will be filled

by the method of Last Observation Carried Forward (LOCF). The missing data of the pre-vaccination antibody result will be filled with the maximum of pre-vaccination antibody results among all the subjects. In terms of the evaluation of the immunogenicity, exploratory, and safety endpoints, missing data will not be filled.

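### SAP 6.5(1): as written, the Phase I between-schedule T-cell comparison takes a log-transformed t-test on a spot-count difference that can be zero or negative, in conflict with the rank-sum test given to the same variable (minor)

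*SAP*

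**What the plan says.** Three parts of SAP section 6.5(1), on Phase I, bear on this.

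- **Positive rates.** T-cell positive rates are tested by chi-square or Fisher, and the paragraph closes with a between-schedule comparison of its own: "Additionally, using the same method, their comparison between emergency immunization schedule and routine immunization schedule will be conducted by group".
- **Quantitative value.** The next paragraph opens "Descriptive statistics for the difference between the average number of stimulation holes for T cell response assay" and continues "and that of negative control on day 14 (emergency immunization schedule) / 28 (routine immunization schedule) after the first dose of immunization". Its tests are explicit: "Rank-sum test will be used to test the difference among groups", and then "pairwise comparison will be conducted between groups by rank-sum test".
- **6-month GMT.** The last paragraph describes the neutralizing-antibody GMT, names a log-transformed t-test as the only test, and moves straight to the T-cell assay: "if statistically significance exists, group t-test with log-transformation will be conducted between groups. Additionally, using the same method, T cell response assay". That final sentence is about comparing the emergency and routine schedules within the medium-dose and high-dose groups.

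Two other sections matter. Section 4.1.2 defines a positive result. When the control average is below 6, "the average number of peptide stimulation wells - negative control" must exceed 6; when the control average is 6 or more, the ratio must be at least 2. Section 6.9 says: "In terms of the evaluation of the immunogenicity, exploratory, and safety endpoints, missing data will not be filled". No section gives an offset, floor or other rule for taking the logarithm of a value at or below zero.

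**The concern.** A background-subtracted count has no lower bound at zero. In a subject with no true response it scatters around zero and is often zero or negative. Rank-sum handles such values; a logarithm does not.

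The between-schedule positive rates already have their own sentence, so the closing sentence most naturally concerns the quantitative value. The nearest method before it is the log t-test. One variable would then have rank-sum within a schedule and a log t-test between schedules, and the second test cannot be computed for part of the data.

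If the undefined logs are set to missing, the comparison covers only subjects whose difference is positive. Those lost are non-responders, and more are lost from the schedule with fewer responders. The analysis set then depends on the outcome, and a difference in the share responding is harder to see. If the analyst instead adds a constant, the choice of constant would be made without a rule, possibly after the data are seen.

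**Working it through.** **Size of the comparison.** Section 3.1 gives 36 subjects per dosage stage and 72 per schedule in Phase I, allocated 2:1. Vaccinees per schedule: 72 × 2/3 = 48, which matches the 48 in section 3.3. Per dose group and schedule: 36 × 2/3 = 24. Each between-schedule comparison is 24 v 24. The SAP states no power, effect size or alpha for it.

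**Who would be dropped.** The SAP gives no background level, responder share or spot distribution, so what follows rests on assumptions: duplicate wells, Poisson counts, non-responders with no true signal.

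For a non-responder, the two well totals are independent Poisson counts with the same mean, so P(difference ≤ 0) = (1 + P(tie)) / 2.

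| Background mean (spots) | P(tie) | P(difference ≤ 0) |
|---|---|---|
| 0.2 | 0.524 | 0.762 |
| 4 | 0.101 | 0.550 |

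Share of an arm dropped ≈ (1 − responder share) × P(difference ≤ 0). With responder shares of 30% v 70%, 40% v 80% and 50% v 90%:

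- Weaker arm: from 0.5 × 0.550 = 0.275 (about 28%) to 0.7 × 0.762 = 0.533 (about 53%).
- Stronger arm: from 0.1 × 0.550 = 0.055 (about 6%) to 0.3 × 0.762 = 0.229 (about 23%).

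**Who would stay.** The section 4.1.2 cut-off is a difference above 6 (or a ratio of at least 2), not a difference above 0. In a simulation with control means 1 to 5, 1 to 3 wells and responder shares of 30% to 90%, 32-63% of subjects negative by that rule had a difference at or below zero. The other 37-68% kept a valid logarithm. No positive subject had a difference at or below zero.

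**Power, first model.** Responders lognormal with median 15 spots and geometric SD 2; 2,000 runs per scenario; two-sided 5%. Entries are log t-test with values ≤ 0 dropped / rank-sum on all values.

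| Background | 30% v 70% | 40% v 80% | 50% v 90% |
|---|---|---|---|
| 0.2 | 0.34 / 0.69 | 0.29 / 0.68 | 0.27 / 0.68 |
| 0.5 | 0.45 / 0.68 | 0.41 / 0.66 | 0.38 / 0.68 |
| 2 | 0.49 / 0.67 | 0.45 / 0.67 | 0.43 / 0.67 |
| 4 | 0.46 / 0.66 | 0.41 / 0.68 | 0.42 / 0.69 |

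The smallest loss is 0.67 − 0.49 = 0.18 and the largest 0.68 − 0.27 = 0.41. With equal shares of 50%, both tests reject in about 5% of runs.

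**Power, second model.** Responders lognormal with median 20 spots and log-SD 0.8; duplicate wells; control mean 1 or 3; 4,000 runs. The third test adds 1 after flooring at zero, so that nobody is lost.

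| Scenario | Rank-sum | Log t, ≤ 0 dropped | Log(x+1) t, floor at 0 |
|---|---|---|---|
| Shares 40 points apart (same three pairs) | 65-68% | 39-47% | 72-79% |
| Shares 60% v 60%, median 20 v 40 | 16% | 17-18% | 12-13% |
| No difference (60% v 60%) | about 5% | 5% | about 5% |

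Of 48 subjects, about 34 to 40 remain on average in the dropped-value analysis.

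**The case against.** **The method is inferred from word order.** The SAP never says in terms that the T-cell value takes a log t-test. In section 6.6.3 (Phase I) the same-method phrase, applied to the antinuclear-antibody positive rate, follows a log-transformed ANOVA, yet it can only mean the chi-square or Fisher test named earlier. The GMT paragraph in 6.5(1) is also disordered: it makes the t-test conditional on significance without naming an overall test, whereas 6.5(2) has an ANOVA step there. A misplaced cross-reference to rank-sum is therefore plausible. This stands as an explanation of how the text arose. It does not remove the point, because the text as written still leads to a test that cannot be applied to all values, and the same edit cures either cause.

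**Responder share is tested elsewhere.** Positive rates are compared between schedules by chi-square or Fisher. The T-cell endpoints listed in 4.1.2 are both positive rates, so the spot-count comparison is supplementary. Section 6.7 makes all p-values nominal. Section 7 also allows slight changes of method if the data distribution turns out unexpectedly. These points stand and limit the importance.

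**The power loss depends on chosen conditions.** It requires dropping, which the SAP does not state, and a difference in responder share. The largest loss comes from a very low assumed background of 0.2 spots. With a floor and an added constant the log test did better than rank-sum in the share scenarios. This also stands; but the SAP states no constant, and the choice is arbitrary.

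**Conclusion.** The point holds as a minor one. Section 6.5(1), read as written, gives one variable two conflicting tests, and the one for the between-schedule comparison is undefined at zero and negative values, with no rule for them.

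If undefined logs are dropped, the assumed models give a loss of about 28-53% of the weaker arm and power of about 27-49% instead of about 65-69%, for 24 v 24 subjects and responder shares 40 points apart. These figures rest on Poisson wells and lognormal responders, none of which is in the SAP. Where only the responders' level differs, the choice of test hardly matters.

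A reader might infer that the test would compare responders only. The documents do not support that: differences above zero but short of the 4.1.2 cut-off keep a valid logarithm, so only some non-responders are lost. Nor do they support saying that the SAP directs subjects to be dropped; that is a software default. Nor would a schedule difference in the share responding go unexamined, since positive rates have their own test.

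**What to change.** In the closing T-cell sentence of section 6.5(1), replace the reference to the same method by: *using the rank-sum test on the stimulated-minus-negative-control difference, zero and negative values retained*. Keep the log-transformed t-test in that paragraph for the 6-month GMT only.

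The cost is one sentence of SAP text. The SAP already assigns the rank-sum test to this variable for the comparison among groups, so no new method and no new data are needed.
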